Protocol description	Written consent will be obtained after complete information of the subjects about the objectives, and the nature and possible risks of the study (informed consent form in duplicate, one copy given to the volunteer). The protocol will be explained in details, with objectives and constraints, according to the information form, by the scientist in charge. A clinical exam and a check-up of all selection criteria will be performed by the main investigator or another medical doctor.  At the inclusion visit, subjects will have a medical exam including questionnaire

	
regarding past medical history, family background, medical treatments and standard clinical exam (weight, height, blood pressure) and a blood sampling. A food frequency questionnaire will also be completed. The conformity to the selection criteria will be checked during this medical exam. The selected subjects will be definitely included after validation of the selection criteria by the investigator.
 
The volunteers will consume in 3 distinct experimental periods either a control drink (oral nutritional complement Fresubin, 250 mL), or 240g banana (and 150 ml Fresubin), or 300g tomato (with 12 g sunflower oil and 150 mL Fresubin). Every volunteer will consume the 3 test foods, in a randomized order. After test food intake, urine will be collected over 24h in 7 fractions. Blood samplings will be performed before the food consumption (t0) and in post-prandial period (4 samplings at 1h, 2h, 4h et 6h), as well as on the following day in fasting state (t24h). the volunteers will follow a tomato and banana-free diet during the study days, as well as a more restrictive diet, without plant-based food, on the sampling days and on the day before. A 24h recall will be filled for the dietary intakes on the day before the sampling days (D2).
 
Samples will be analyzed using an untargeted metabolomics approach (LC-MS, GC-MS et RMN) with the aim to identify new biomarkers of tomato and banana intake.
 
The total volume of sampled blood will be 154 ml per subject.

Duration	
Duration of the study for every volunteer : 8 weeks
 
Total duration of the study: 6 months for the subject selection and realization of all experimental periods for all the volunteers
 
Total duration of the project : 3 years

Indemnities	350€ per subject

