### **4 – PROTOCOL DESCRIPTION**

The present project is a randomized, controlled, crossover study with 12 subjects. A cross-over design has been selected as each subject can serve as his/her own control thereby minimizing variations. Limitations attributed to cross-over designs are possible order or carry-over effects. These effects will however be minimized due to a randomized intervention order. The study design does not allow blinding as intervention is the ingestion of different foods.

In this study, we will assess the metabolomic profiles of human biofluids after consumption of two different foods: banana (240g peeled fruit) and tomato (300g fresh fruit) in order to identify novel biomarkers for each food. As a control diet, a high energy high protein drink, Fresubin ® 2kcal fiber (Fresinius kabi) will be used. As shown in the general study plan, the intervention comprises three dietary intervention periods of 4 days each for each food of interest and the control drink. Each

intervention period will be separated by a washout period of minimum 3 days (and maximum 10 days). Volunteers will be randomly assigned to a different food at each time point. Volunteers will be asked to maintain their normal physical activity and follow the dietary recommendations between intervention periods; they will receive an information form containing the description and objectives of the project, and detailed instructions. A volunteer’s booklet will also include simple information about nutritional metabolomics and a calendar marked with their visits to our facilities.

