### 6-3 BIOLOGICAL SAMPLES

#### 6-3-1 Blood samples

We will collect 6 blood samples (8 ml), one at baseline and 5 others after the acute intervention (t= 0hr, 1hr, 2hr, 4hr, 6hr, 24hr) at each of the 3 experimental interventions (Banana, Tomato, Control drink Fresubin). These samples will be collect at the Unité d'Exploration Nutritionnelle and will be stored at the Human Nutrition Unit, INRA Centre of Theix. Volunteers will arrive at the Investigation Center in an 8-12 hour fasting state and after two days of a restricted diet. All blood samples will be processed immediately after they are drawn allowing clotting at room temperature for 30 minutes. After clotting serum will be collected in aliquots and then stored at -80°C until analysis. The whole volume of blood collected during the experimental periods is 8mL x 6 time points x3 experimental periods = 144 mL. In addition, 10 mL blood will have been collected at the screening visit. The sample collected at the screening visit will be analysis the same day of the collect by the Biochemistry Unit of Clermont Ferrand Hospital.

In total, the volume of blood collected for the whole BioBanaTom study is 154 mL.

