Projet BioBanaTom “Identification of new biomarkers of banana and tomato intake”

Protocol ID: 2016-A00153-48

Statistical Analysis for urinary and plasma metabolome changes

after banana and tomato intake

Version 2 – 25/06/2018

The statistical analysis is centralized and performed by the INRA investigators, in close collaboration with the statistician of the Metabolomics platform ([name] INRA, [name], PFEM: Plateforme d’Exploration du Métabolisme).

The dataset resulting for, the urine samples of the clinical trial, ion intensities is normalized according to the volume collected for each urine fraction. A PCA model is applied to the normalized dataset to detect possible outliers in the dataset. Q primary PLSDA model is built using the three interventions as “Y” variables. The dataset are also assessed separately for banana versus control and tomato versus control.

To better discriminate the ions according to the intake of banana, an OSC-PLSDA model is built with the dataset containing control and banana samples (n=24). Statistical analysis is performed with SIMCA-P+ software (version 14.0, Umetrics, Umea, Sweden). The OSC filter is built with log transformed and Pareto scaled data using treatment (banana vs control; tomato vs control) as correction factor. A k-fold cross validation method is used with 4 subsets to predict the ability of the model to correctly classify samples to the corresponding dietary treatment. Q^2 is used to assess the prediction power and to determine the reliability of the model a permutation test (n= 500) is carried out.

Simultaneously, the difference in intensity of the extracted features between dietary treatments is assessed by applying a Student T test with Benjamini Hochberg correction (BH) for multiple comparisons using Metaboanalyst 3.0 [20]. Significance level is established at p value BH <0.05. Those features with a variable importance of projection (VIP) higher than 2 in the OSC-PLS-DA model, a T-test with BH p value <0.05 and which present in higher intensity in the urinary samples of the banana group are prioritized for identification as candidate biomarkers of banana intake. The same strategy is applied for the tomato dataset.

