The dataset resulting from the analysis of plasma samples is assessed separately for banana and tomato versus control. Principal component analysis is performed for the detection of outliers in the dataset. For a first selection of ions, a one way ANOVA with a post hoc between the different time points is

applied using SPSS IBM version 22. Ions that were higher and significantly different than time point 00h (p value <0.01) are selected to be analyzed using a PLSDA model using SIMCA-P (version 14.0, Umetrics, Umea, Sweden). Ions with a VIP>2 and in higher intensity in banana or tomato are selected as plausible biomarkers of intake.

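### The plasma one-way ANOVA across time points has no subject term although each subject supplies all six samples, so ions with rises of about 1 SD can be missed

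*SAP*

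**What the plan says.** Protocol section 6-3-1 fixes the blood schedule for each of the three foods: "We will collect 6 blood samples (8 ml), one at baseline and 5 others after the acute intervention", at 0, 1, 2, 4, 6 and 24 h. Protocol section 4 gives the reason for the design: "A cross-over design has been selected as each subject can serve as his/her own control thereby minimizing variations".

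The plasma part of the SAP starts with "a one way ANOVA with a post hoc between the different time points", run in SPSS. The selection rule is: "Ions that were higher and significantly different than time point 00h (p value <0.01) are selected to be analyzed using a PLSDA model". No subject, repeated-measures or random term is named. The post hoc method is not named, and no multiplicity correction is stated for this step. Protocol section 9 names ANOVA with a Benjamini-Hochberg correction, also without a subject term.

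The urine part of the SAP uses "a Student T test with Benjamini Hochberg correction (BH) for multiple comparisons using Metaboanalyst 3.0" on a banana-and-control dataset of 24 samples, with the same strategy for tomato. It does not say whether the test is paired. The protocol summary states that "urine will be collected over 24h in 7 fractions"; the SAP does not say how these become one value per subject per food.

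**The concern.** A one-way ANOVA treats the samples at the six times as six independent groups. Here they are repeated samples from the same people. If a person's level of an ion is partly stable over the day, that stable part cancels when a later sample is compared with the same person's 0 h sample. The one-way error term keeps it. The test then uses a standard error that is too large for the comparison being made.

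The step matters because it comes first: an ion that fails it never reaches the PLS-DA, so no later step can recover it. The trial has 12 subjects, aims for 10 completers and, by protocol section 5-2, has no power calculation. The choice of error term therefore carries much of the sensitivity for identifying biomarkers, which is the primary endpoint.

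**Working it through.** **Plan's own figure.** The only sample count in the SAP is the urine n=24. 12 subjects x 2 foods = 24, so it fits one value per subject under each condition, that is, 12 pairs. It fits two groups of 12 equally well, so it does not settle whether the t-test is paired.

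**Inputs for plasma.** From the documents: 12 subjects (10 completers as the aim), six times, p<0.01 against 0 h. Assumed, because the documents give none of them: normal log intensity with SD 1 at every time, one common within-subject correlation ρ of 0, 0.3, 0.5 or 0.7, a rise of d SD at one time, an LSD post hoc, and an ANOVA run on one food's samples.

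**Degrees of freedom.** 12 x 6 = 72 samples.
- One-way ANOVA: 72 − 6 = 66
- Subject as a block: 66 − 11 = 55
- Paired contrast: 12 − 1 = 11

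**Standard error of a difference from 0 h.**
- Used by the one-way ANOVA: √(2/12) = 0.408 SD, whatever ρ is
- Actual: √(2(1−ρ)/12) = 0.408 / 0.342 / 0.289 / 0.224 SD at ρ = 0 / 0.3 / 0.5 / 0.7

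With critical t 2.652 on 66 df, the one-way test needs an observed rise of about 2.652 x 0.408 = 1.08 SD. That is why its power at a true 1 SD rise stays just above 40% at every correlation.

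**Power at p<0.01, d = 1.** The blocked and paired tests use the noncentral t with noncentrality d√(12/(2(1−ρ))) = 2.449 / 2.928 / 3.464 / 4.472 and critical t 2.668 (55 df) or 3.106 (11 df). The one-way test was simulated (100,000 runs).

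| ρ | 0 | 0.3 | 0.5 | 0.7 |
|---|---|---|---|---|
| As written | 42.2% | 41.7% | 41.2% | 40.6% |
| Subject-blocked | 42.1% | 60.4% | 78.3% | 96.1% |
| Paired contrast | 31.3% | 46.6% | 64.2% | 88.5% |
| True type I as written (nominal 1%) | 1.0% | about 0.3% | about 0.07% | about 0.01% |

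**Larger effects, same threshold.**
- d = 1.5: as written 84.2 / 88.0 / 90.7 / 93.5%; blocked 83.8 / 95.4 / 99.3 / >99.9%; paired 70.5 / 87.1 / 96.4 / 99.9%.
- d = 2: as written at least 98% throughout.

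**Ten completers, d = 1.** As written about 34 / 32 / 31 / 30%; blocked 34 / 50 / 68 / 91%; paired 23 / 35 / 50 / 77%.

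**Post hoc method.** With Tukey instead of LSD (12 subjects, d = 1, ρ = 0.5), power is about 11% as written and 48% blocked. The level depends on the unnamed method; the direction does not.

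**Adding a multiplicity correction.** Take 5e-4 as an illustrative Benjamini-Hochberg cut-off (0.05 x 20/2000, that is, about 20 of an assumed 2,000 ions called). Paired contrasts at 5e-4, against the plan's uncorrected p<0.01:
- d = 1: 5 / 10 / 18 / 43%, against about 42 / 42 / 41 / 41%
- d = 1.5: 23 / 41 / 63 / 91%, against the as-written figures above

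**The case against.** **The wording may be shorthand.** A one-way ANOVA over time can mean a one-factor repeated-measures ANOVA. That cannot be ruled out. But someone following the SAP would run the ordinary one-way procedure, and nothing elsewhere points to another reading. If repeated measures was meant, one sentence closes the point.

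**The markers sought may be unaffected.** Banana and tomato are excluded during the run-in and most plant foods on Day 2. A food-specific ion may therefore sit near background at 0 h, with little within-subject correlation, and then rise sharply. This largely stands. At zero correlation blocking gains nothing and pairing costs power (31% against 42%); pairing breaks even at a correlation of about 0.2. At 2 SD the plan already succeeds. The loss is confined to rises of about 1 SD with positive correlation.

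**Within-subject contrasts plus Benjamini-Hochberg detect less than the plan.** This is correct for rises of 1 to 1.5 SD at correlations 0 to 0.5 and the assumed cut-off. A reader might take the power gain as belonging to the combined change. It holds only at equal thresholds; the correction buys fewer false positives at a cost in power.

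**Repeated samples treated as independent usually give false positives.** A reader might infer that here. It does not follow from the missing subject term: each subject contributes one sample to every time point, so with similar variances and positive correlation each comparison becomes too strict, not too lenient.

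**Conclusion.** The point holds for plasma. As written, the first ion filter has an error term that does not match six repeated samples from the same subjects, and it gives up the advantage the protocol cites for the crossover. At p<0.01 with 12 subjects and a 1 SD rise, the shortfall against a subject-blocked analysis is nil at correlation 0, about 19 points at 0.3 (60.4 − 41.7), 37 at 0.5 (78.3 − 41.2) and 56 at 0.7 (96.1 − 40.6). At 1.5 SD it is at most about 9 points (99.3 − 90.7), and at 2 SD it is negligible. Correlation, SD, effect size and post hoc method are all assumed. How many more ions would reach the final list cannot be known, because the VIP and direction rules also apply.

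For urine there is only a missing statement. A reader might infer that the t-test is unpaired, but a dataset of 24 is consistent with 12 pairs and the SAP says neither.

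**What to change.** **Plasma.** Replace the one-way ANOVA with a repeated-measures analysis on log intensity (subject as a block or random effect, sphericity correction for the overall test). Contrast each time point with the same subject's 0 h sample, and name the post hoc method. Use paired contrasts where variances or correlations differ over the 24 h. For example, if the correlation with 0 h falls from 0.69 at 1 h to 0.47 at 4 h and 0.20 at 24 h (assumed), pooled-error contrasts have true type I error of 0.06 / 0.8 / 3.0% at nominal 1%, against 1.0% for paired contrasts at all three. If repeated measures was already intended, say so.

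**Multiplicity.** Decide separately whether the correction named in protocol section 9 applies to this step, and justify it on false positives, not power.

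**Urine.** State that the t-test on the 12 food-control pairs is paired, and how the fractions become one value per subject per food.

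**Cost.** SAP wording and one re-run of the plasma screen and the PLS-DA that follows it; no new data. Paired contrasts lose some power for ions with correlation below about 0.2.

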## SUMMARY

Promotor	INRA
Main investigator	[name]
Co-Investigators	[name], [name], [name]
Title	Identification of new biomarkers of banana and tomato intake
Rational	In epidemiological studies, dietary intakes are assessed by questionnaires, an approach with inherent limitations associated with self-reporting : memory bias, difficulty to estimate portion size, insufficient coverage of the dietary diversity... The use of biomarkers of food intake should markedly improve the accuracy of dietary assessment, However, only few validated biomarkers are available. A large European project (FoodBALL) was funded by the JPI HDHL to identify a large range of new biomarkers of intakes, using untargeted metabolomics on urine and plasma samples collected in a series of controlled nutritional intervention studies.
Objective	The BioBanaTom study aims, in the framework of the FoodBALL project, at identifying new biomarkers of intake for banana and tomato, two important foods of the European diet.
Evaluation criteria	Main Criteria: Identification using metabolomics of plasma and urine metabolites specifically associated to banana and tomato intake, for validation as biomarkers. Secondary criteria : Obtention of reference metabolomics profiles which may be related to metabolic impact of an acute intake of tomato or banana.
Methodology	Cross-over randomized, open, controlled
Number of subjects	12
Undesirable effects	No undesirable effect expected beyond those link to blood sampling (small local hematoma, slight local inflammation)
Recruitment modalities	Volunteer file of UEN declared to the CNIL, mailing CHRU and INRA Clermont-Ferrand-Theix, local medias. The selection of the volunteers will be performed during medical inclusion visits.
Main selection criteria	Inclusion criteria Men and women, healthy (normal medical and biological exam), non-smoking, aged 18 to 40, BMI>18,5 and <30 kg/m  , with no aversion for banana or tomato. Exclusion criteria Smokers, diagnosed with infectious or chronic disease, under medication (except contraception pill), having followed an antibiotic treatment in the last 3 months, consuming dietary supplements several times a week, pregnant and lactating women, vegetarian as the protocol implies consumption of standardized meal containing meat.

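### The plasma selection rule sets no error rate for food versus control, whereas the urine rule requires a BH-corrected treatment test

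*SAP*

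**What the plan says.** The Protocol's main criterion (Summary, evaluation criteria) is the same for both fluids: "plasma and urine metabolites specifically associated to banana and tomato intake, for validation as biomarkers". Section 7-1-1 makes the endpoint a comparison of metabolomes after tomato, banana or control drink. Blood is drawn six times per period, "one at baseline and 5 others after the acute intervention (t= 0hr, 1hr, 2hr, 4hr, 6hr, 24hr").

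**Urine (SAP).** A candidate must have a VIP above 2 in the OSC-PLS-DA, and also "a T-test with BH p value <0.05 and which present in higher intensity in the urinary samples of the banana group". The t test compares dietary treatments. The model is checked too: "A k-fold cross validation method is used with 4 subsets", Q² is reported, and "to determine the reliability of the model a permutation test (n= 500) is carried out". The SAP extends this strategy to the tomato dataset, and the sentence stands within the urine description.

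**Plasma (SAP, last paragraph).** Each food is set against control. The first step is a one-way ANOVA with a post hoc across time points: "Ions that were higher and significantly different than time point 00h (p value <0.01) are selected to be analyzed using a PLSDA model". The last step is: "Ions with a VIP>2 and in higher intensity in banana or tomato are selected as plausible biomarkers of intake". Nothing further is required.

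**The concern.** The plasma p value answers whether an ion rises after the meal. The main criterion asks whether it is specific to banana or tomato. All three arms contain Fresubin (250 mL alone, 150 mL with either food), so an ion that responds to any meal can pass the time screen.

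What remains is VIP above 2 and direction. That filter does use treatment, but VIP ranks ions against the others in the same model and has no error level attached. Plasma and urine candidates would therefore rest on different evidence under one criterion, and the rule itself would not say how many plasma ions to expect by chance. A false ion costs identification and validation work. A true ion crowded out of the VIP ranking is not followed up.

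**Working it through.** **1. The two rules side by side**

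| Element | Urine | Plasma |
|---|---|---|
| Test of food versus control | Student t test | none named |
| Correction across ions | BH, p < 0.05 | none named |
| Test against 00h | none named | post hoc, p < 0.01 |
| VIP > 2 and higher in food | required | required |
| Cross-validation | 4 subsets | none named |
| Permutation | 500 | none named |

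**2. Document arithmetic.** The urine text gives "an OSC-PLSDA model is built with the dataset containing control and banana samples (n=24"), which reproduces as 12 subjects × 2 treatments = 24. For plasma, 6 times × 12 subjects × 2 arms = 144 samples per comparison if all enter. The plasma paragraph gives no count.

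**3. What the p < 0.01 screen controls.** There are five comparisons with 00h, and half of each two-sided 0.01 is upward. A flat ion passes with probability of at most about 5 × 0.005 = 0.025. That bounds errors about time. It says nothing about an ion that truly rises after any meal.

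**4. What VIP > 2 controls.** Squared VIPs average 1 across the ions in a model. For one PLS component on unit-variance ions with no treatment difference, VIP² behaves approximately as chi-square with 1 df:
- P(VIP > 2) = P(χ²₁ > 4) = 0.0455
- also higher in the food arm: 0.0455 / 2 = 0.0228
- with 300 such ions screened in: 300 × 0.0228 = 6.8 listed by chance

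The 2.3% follows from these assumptions. The SAP does not set it as a level.

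**5. How far the count moves.** The following assumptions are not in the documents: 2000 ions, 300 of them rising 1.5 SD after every meal, within-subject correlation 0.5, unit-variance scaling, unadjusted post hoc. The response ratio is the size of the generic rise in the food arm divided by that in control. Ranges span ANOVA on the food arm or both arms, a flat or peaked time profile, and visit variance 0 or 0.2, where these were varied.
- Time screen: 278–300 of the 300 generic ions pass at ratio 1.0, and 90–300 at ratio 0.6.
- No food ion, one component: about 6–7 false ions at ratio 1.0, 0.15–2.4 at 0.9, none at 0.6.
- No food ion, two components: up to about 7 at ratio 0.6, and 1.9–9.4 at 0.8.
- Ten food ions of 1.5 SD, ratio 1.0, one component: 0–5 false ions.
- Ten food ions of 1.5 SD, ratio 0.6, one component: no false ion, but only 1.7–5.7 of the ten are kept. With food ions of 2.5 SD, 4.9–10 are kept.

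The documents do not fix the ratio. The figure 150/250 = 0.6 is a ratio of drink volumes. The food arms add 240 g banana, or 300 g tomato with 12 g oil, so it is not a meal-response ratio.

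**6. The repair under the same assumptions.** A three-arm model (subject, period, treatment, 00h covariate) on the 1–6h mean, with one-sided BH over 2000 ions, keeps 8.1–10 of ten 1.5-SD food ions at ratio 0.6. With no food ion, it lists any false ion in no more than about 8% of runs.

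**The case against.** The strongest reply is that this is discovery work. The plasma output is described only as plausible biomarkers, validation follows, no error rate is claimed, and section 5-2 declines a single power calculation. This stands as a limit on the harm. It does not explain why urine, which is also discovery, carries a BH test and two model checks while plasma carries none.

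A reader might infer that the plasma analysis never compares food with control, or that a test against 00h is out of place. The documents do not support either reading. Each food is assessed against control, the final step asks for higher intensity in the food, and a time screen fits sections 7-1-1 and 9. The gap is error control on the comparison.

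A reader might also infer that section 9 promised BH for food versus control and the SAP dropped it. Section 9 ties ANOVA with BH to variation along time. Carrying it into plasma would control the time effect only, so it neither sets the missing standard nor closes the gap.

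Control-arm samples exist at all six times, so generic risers can be inspected afterwards. That is true, but inspection is not part of the written rule. The simulated counts are also unstable, which is accepted below. Finally, the fix leaves the rules not quite identical, since urine keeps VIP > 2 as a requirement. What it equalises is the presence of a corrected treatment test and of model checks.

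**Conclusion.** The point holds on the text alone. The only plasma p value is against 00h, and VIP > 2 with direction is then enough to list an ion. The rule therefore sets no false-candidate rate for food specificity, while the urine rule has a BH-corrected treatment test.

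The size is illustrative. With equal meal responses, no food ion and one component, about 2.3% of screened ions are listed by chance, or 6–7 of 300. A reader might infer that each plasma list will hold about seven false ions. The documents do not support that: across settings the count ran from none to about seven, and to about nine in one two-component setting. It depends on response ratio, time profile, visit variance, number of components and presence of true food ions.

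Nor does this point to a wrong confirmatory conclusion. The consequence is false leads and possibly missed true ions. The ANOVA arms and the post hoc method are also unstated, but that is missing detail and not part of the main point. The change is worth making because it is cheap and the main criterion covers both fluids.

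**What to change.** Amend the plasma paragraph of the SAP as follows.
- For each ion, test the within-subject food-minus-control difference in log intensity over a pre-specified post-dose window. Take it from one mixed model on all three arms with subject, period, treatment and the 00h value as covariate.
- Apply BH over all plasma ions, not only those that pass the time screen. Call an ion a candidate only if the contrast is positive with BH p < 0.05, and state whether the test is one- or two-sided.
- Apply the 4-subset cross-validation and 500 permutations to the plasma PLS-DA, keeping each subject's samples together (12 / 4 = 3 subjects per subset).
- Report ions that meet only the 00h screen and VIP > 2 as a separate exploratory list with no error-rate claim.
- Name the arms in the ANOVA and the post hoc method.

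The three-arm form matters. In the illustration with a peaked profile, visit variance 0.2 and ratio 0.6, ten 1.5-SD ions and the 10 completers aimed for, it kept 5.4 ions. A two-arm contrast kept 1.5 and the current rule 1.2–1.8.

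The cost is SAP wording and a little more analysis, with no new samples. Some weak true ions may move to the exploratory list: of ten 1-SD ions with 12 subjects, same profile, visit variance and ratio, the three-arm contrast kept 1.6 and the current rule 0.1–0.6. The SAP should also state that this contrast cannot separate the fruit from the differences in drink volume or oil.
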